2.2.2. Estimand for Secondary Endpoints

The secondary clinical questions of interest are: What is the treatment effect on each of the secondary efficacy endpoints after 5 days treatment with gepotidacin 1500 mg twice daily compared to 5 days treatment with nitrofurantoin 100 mg twice daily in participants with acute cystitis (clinical endpoints) and in participants with acute cystitis with qualifying uropathogen(s) at Baseline that all are susceptible to nitrofurantoin (therapeutic, clinical, and microbiological endpoints), regardless of treatment discontinuation for any reason. Receipt of systemic antimicrobials impacts the endpoint definitions (see Section 7.2.1.1, Section 7.2.1.2, and Section 7.2.1.3).

For each of the secondary efficacy endpoints the estimand will follow a similar approach to the estimand for the primary endpoint and use the same strategies for the intercurrent events. The exception is the summary measure for the outcome endpoints. These endpoints are descriptively summarized and therefore the summary measure will be the percentage in each clinical and microbiological outcome category in the gepotidacin and nitrofurantoin arms separately (as no direct comparison between treatment groups will be made).

The safety endpoint will use a treatment policy strategy for the intercurrent event of withdrawal from treatment since the safety will be assessed at all post baseline assessments irrespective of whether the patient completed the treatment. Components of estimand for all secondary endpoints are listed in [Table 1](#).

Table 1 Estimand for Secondary Endpoints

	Population	Treatment condition	Variable	Summary measure	ICE
Clinical response at the TOC and FU Visits	Female participants with acute cystitis	Gepotidacin 1500 mg twice daily for 5 days versus nitrofurantoin 100 mg twice daily for 5 days regardless of adherence.	See Table 8 (Section 7.1.1) and Table 11 (Section 7.2.1)	Difference in the Clinical success rate in the gepotidacin and nitrofurantoin treatment groups.	Study treatment discontinuation (due to any reason) – treatment policy Use of systemic antimicrobials - composite strategy
Clinical outcome at the TOC and FU Visits	Female participants with acute cystitis	Gepotidacin 1500 mg twice daily for 5 days versus nitrofurantoin 100 mg twice daily for 5 days regardless of adherence.	See Table 8 (Section 7.1.1) and Table 11 (Section 7.2.1)	Percentage of participants in each outcome category in the gepotidacin and nitrofurantoin arms separately	Study treatment discontinuation (due to any reason) – treatment policy Use of systemic antimicrobials - composite strategy
Clinical response at the TOC and FU Visits	Female participants with acute cystitis with qualifying uropathogen(s) at Baseline that all are susceptible to nitrofurantoin.	Gepotidacin 1500 mg twice daily for 5 days versus nitrofurantoin 100 mg twice daily for 5 days regardless of adherence.	See Table 8 (Section 7.1.1) and Table 11 (Section 7.2.1)	Difference in the Clinical success rate in the gepotidacin and nitrofurantoin treatment groups.	Study treatment discontinuation (due to any reason) – treatment policy Use of systemic antimicrobials - composite strategy

CONFIDENTIAL

212390

[figure not shown]
	Population	Treatment condition	Variable	Summary measure	ICE
Clinical outcome at the TOC and FU Visits	Female participants with acute cystitis with qualifying uropathogen(s) at Baseline that all are susceptible to nitrofurantoin	Gepotidacin 1500 mg twice daily for 5 days versus nitrofurantoin 100 mg twice daily for 5 days regardless of adherence	See Table 8 (Section 7.1.1) and Table 11 (Section 7.2.1)	Percentage of participants in each outcome category in the gepotidacin and nitrofurantoin arms separately	Study treatment discontinuation (due to any reason) – treatment policy Use of systemic antimicrobials - composite strategy
Microbiological response at the TOC and FU Visits	Female participants with acute cystitis with qualifying uropathogen(s) at Baseline that all are susceptible to nitrofurantoin.	Gepotidacin 1500 mg twice daily for 5 days versus nitrofurantoin 100 mg twice daily for 5 days regardless of adherence.	See Table 7 (Section 7.1.1) and Table 10 (Section 7.2.1)	Difference in the microbiological success rate in the gepotidacin and nitrofurantoin treatment groups.	Study treatment discontinuation (due to any reason) – treatment policy Use of systemic antimicrobials - composite strategy
Microbiological outcome at the TOC and FU Visits	Female participants with acute cystitis with qualifying uropathogen(s) at Baseline that all are susceptible to nitrofurantoin.	Gepotidacin 1500 mg twice daily for 5 days versus nitrofurantoin 100 mg twice daily for 5 days regardless of adherence.	See Table 7 (Section 7.1.1) and Table 10 (Section 7.2.1)	Percentage of participants in each outcome category in the gepotidacin and nitrofurantoin arms separately	Study treatment discontinuation (due to any reason) – treatment policy Use of systemic antimicrobials - composite strategy
Therapeutic response at the FU Visit	Female participants with acute cystitis with qualifying uropathogen(s) at Baseline that all are susceptible to nitrofurantoin.	Gepotidacin 1500 mg twice daily for 5 days versus nitrofurantoin 100 mg twice daily for 5 days regardless of adherence.	See Table 10 and Table 11 (Section 7.2.1)	Difference in the therapeutic success rate in the gepotidacin and nitrofurantoin treatment groups.	Study treatment discontinuation (due to any reason) – treatment policy Use of systemic antimicrobials - composite strategy

CONFIDENTIAL

212390

	Population	Treatment condition	Variable	Summary measure	ICE
Safety	Female participants with acute cystitis	Gepotidacin 1500 mg twice daily for 5 days versus nitrofurantoin 100 mg twice daily for 5 days regardless of adherence.	TEAEs, SAEs, as well as change from baseline results for clinical laboratory tests, and vital sign measurements.	Summary statistics (appropriate for each type of endpoint) in the gepotidacin and nitrofurantoin arms separately	Study treatment discontinuation (due to any reason) – treatment policy

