3. OBJECTIVES AND ESTIMANDS/ENDPOINTS

Objectives	Endpoints

Primary
 
 To assess the combined clinical and microbiological efficacy of gepotidacin compared to nitrofurantoin, at the TOC Visit, in female participants with acute cystitis with qualifying bacterial uropathogen(s) at Baseline that all are susceptible to nitrofurantoin 	
 Therapeutic response (combined per-participant microbiological and clinical response) at the TOC Visit

Secondary
 
 To assess the clinical efficacy of gepotidacin compared to nitrofurantoin, at the TOC and Follow-up Visits, in female participants with acute cystitis To assess the clinical efficacy of gepotidacin compared to nitrofurantoin, at the TOC and Follow-up Visits, in female participants with acute cystitis with qualifying bacterial uropathogen(s) at Baseline that all are susceptible to nitrofurantoin To assess the microbiological efficacy of gepotidacin compared to nitrofurantoin, at the TOC and Follow-up Visits, in female participants with acute cystitis with qualifying bacterial uropathogen(s) at Baseline that all are susceptible to nitrofurantoin To assess the combined clinical and microbiological efficacy of gepotidacin compared to nitrofurantoin, at the Follow-up Visit, in female participants with acute cystitis with qualifying bacterial uropathogen(s) at Baseline that all are susceptible to nitrofurantoin 	
 Clinical outcome and response at the TOC and Follow-up Visits Clinical outcome and response at the TOC and Follow-up Visits Microbiological outcome and response at the TOC and Follow-up Visits Therapeutic response (combined per-participant microbiological and clinical response) at the Follow-up Visit

Objectives	Endpoints

Secondary continued
 
To assess the safety and tolerability of gepotidacin compared to nitrofurantoin in female participants with acute cystitis	
Treatment-emergent AEs and serious AEs (SAEs) and change from baseline results for clinical laboratory tests, electrocardiograms (ECGs), and vital sign measurements

Objectives	Endpoints
CCI	

Primary Estimand

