Microbiological response at the TOC and Follow-up Visits	Female participants with acute cystitis with qualifying bacterial uropathogen(s) at Baseline that all are susceptible to nitrofurantoin	Gepotidacin 1500 mg BID for 5 days versus nitrofurantoin 100 mg BID for 5 days, regardless of adherence	See Table 5	Absolute difference in the microbiological success rate in the gepotidacin and nitrofurantoin treatment groups	Study treatment discontinuation (due to any reason) – treatment policy Use of systemic antimicrobials – composite strategy
Microbiological outcome at the Follow-up Visit	Female participants with acute cystitis with qualifying bacterial uropathogen(s) at Baseline that all are susceptible to nitrofurantoin	Gepotidacin 1500 mg BID for 5 days versus nitrofurantoin 100 mg BID for 5 days, regardless of adherence	See Table 5	Percentage of participants in each outcome category in the gepotidacin and nitrofurantoin arms separately	Study treatment discontinuation (due to any reason) – treatment policy Use of systemic antimicrobials – composite strategy
Therapeutic response at the Follow-up Visit	Female participants with acute cystitis with qualifying bacterial uropathogen(s) at Baseline that all are susceptible to nitrofurantoin	Gepotidacin 1500 mg BID for 5 days versus nitrofurantoin 100 mg BID for 5 days, regardless of adherence	See Table 5 and Table 11	Absolute difference in the therapeutic success rate in the gepotidacin and nitrofurantoin treatment groups	Study treatment discontinuation (due to any reason) – treatment policy Use of systemic antimicrobials – composite strategy
Safety	Female participants with acute cystitis infection	Gepotidacin 1500 mg BID for 5 days versus nitrofurantoin 100 mg BID for 5 days, regardless of adherence	TEAEs, SAEs, as well as change from baseline results for clinical laboratory tests, ECGs, and vital sign measurements	Summary statistics (appropriate for each type of endpoint) in the gepotidacin and nitrofurantoin arms separately	Study treatment discontinuation (due to any reason) – treatment policy

BID=twice daily; EGG=electrocardiogram; SAE=serious adverse event; TEAE=treatment-emergent adverse event; TOC=Test-of-Cure.

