9.4.3. Safety Analyses

All safety analyses will be performed on the Safety Population. The severity of AEs and SAEs will be determined by the investigator according to the US National Institute of Allergy and Infectious Diseases Division of Microbiology and Infectious Diseases (DMID) criteria for adult toxicity assessment [DMID, 2007a], with the exception of serum creatinine adolescent laboratory data, which will be assessed using pediatric toxicity criteria [DMID, 2007b] (Appendix 13). All reported AEs will be coded using MedDRA and summarized by system organ class and preferred terms.

Estimands/Endpoints	Statistical Analysis Methods
Secondary	
 The safety endpoint will use a treatment policy strategy for the ICE of withdrawal from treatment, as safety will be assessed at all postbaseline assessments irrespective of whether the participant completed the treatment.

Estimands/Endpoints	Statistical Analysis Methods
	
 • The number and percentage of treatment-emergent AEs, study treatment-related AEs, deaths, SAEs, and AEs leading to study treatment or study withdrawal will be provided. • Treatment-emergent AEs will be summarized by severity. • Change from baseline over time in laboratory parameters, ECGs, and vital signs will be summarized with descriptive statistics. Note: Electrocardiograms will be centrally overread for the data analysis. • The frequency of laboratory abnormality events along with the shift from baseline to the worst-case postbaseline value will be provided. Abnormal liver chemistry results will be determined using increases above the upper limit of normal. Change from baseline values will be summarized with descriptive statistics. • The severity of specified AEs and laboratory abnormalities will be graded according to the modified DMD toxicity grading system (Appendix 13). Data will be tabulated and reported by absolute grade for Grades 3 and higher and shift tables, as appropriate. • Adverse events of special interest will include CV, gastrointestinal, and C. difficile infection or colitis events. In addition, AEs associated with acetylcholinesterase inhibition are also considered special interest. As described in the RAP, manual and programmatic reviews of AEs/preferred terms will be used to assess these events.

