2. SUMMARY OF KEY PROTOCOL INFORMATION

2.1. Changes to the Protocol Defined Statistical Analysis Plan

Changes to the planned statistical analysis specified in the protocol (Dated: 03-NOV-2021) are listed below.

- Whilst demonstration of NI at the final analysis (if the study continues at the IA) will remain based on the primary analysis only, the IA recommendation framework at the IA has been updated to include a supplementary analysis performed on a supplementary analysis population defined as the primary analysis population excluding participants from investigators/sites which have had a corrective and preventative action (CAPA) put in place requiring that a supplementary analysis excluding data from these sites be performed. This population will be labeled micro-ITT NTF-S (CAPA) population and will be performed on the IA Set if applicable. The updated IA recommendation framework requires both the primary and supplementary analyses to meet the NI boundary to stop the study for efficacy at the interim analysis. If the study continues at the interim analysis, demonstration of NI at the final analysis will remain based on the primary analysis only (micro-ITT NTF-S) and the supplementary analysis (micro-ITT NTF-S (CAPA)) performed at the final analysis will be provided for descriptive purposes only. This is detailed in Section 2.4 and Section 5.5.
 - Note: At the IA, for testing futility against the boundary only the primary population (micro-ITT NTF-S (IA Set) population) should be used to determine if the futility boundary has been met. The micro-ITT NTF-S (CAPA) (IA Set) supplementary analysis will also be available to the IDMC. The Z-Statistic boundaries in this supplementary analysis will be consistent with the primary analysis and presented for reference (i.e., should not be used as formal hypothesis testing for futility).
 - Note: Sensitivity analyses (i.e., unadjusted treatment difference and treatment difference adjusting for strata as randomized) will also be available to the IDMC. The Z-Statistic boundaries (for efficacy and/or futility) in these sensitivity analyses will be consistent with the primary analysis and presented for reference (i.e., should not be used as formal hypothesis testing).

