2.2. Study Objective(s) and Estimand(s) / Endpoint(s)

Objectives	Endpoints
Primary	Primary
To assess the combined clinical and microbiological efficacy of gepotidacin compared to nitrofurantoin, at the Test-of-Cure (TOC) Visit, in female participants with acute cystitis with qualifying uropathogen(s) at Baseline that all are susceptible to nitrofurantoin	Therapeutic response (combined per-participant microbiological and clinical response) at the TOC Visit.
Secondary	Secondary
To assess the clinical efficacy of gepotidacin compared to nitrofurantoin, at the TOC and Follow-up Visits, in female participants with acute cystitis	Clinical outcome and response at the TOC and Follow-up Visits.
To assess the clinical efficacy of gepotidacin compared to nitrofurantoin, at the TOC and Follow-up Visits, in female participants with acute cystitis with qualifying uropathogen(s) at Baseline that all are susceptible to nitrofurantoin	Clinical outcome and response at the TOC and Follow-up Visits.
To assess the microbiological efficacy of gepotidacin compared to nitrofurantoin, at the TOC and Follow-up Visits, in female participants with acute cystitis with qualifying uropathogen(s) at Baseline that all are susceptible to nitrofurantoin	Microbiological outcome and response at the TOC and Follow-up Visits.
To assess the combined clinical and microbiological efficacy of gepotidacin compared to nitrofurantoin, at the Follow-up Visit, in female participants with acute cystitis with qualifying uropathogen(s) at Baseline that all are susceptible to nitrofurantoin	Therapeutic response (combined per-participant microbiological and clinical response) at the Follow-up Visit.
To assess the safety and tolerability of gepotidacin compared to nitrofurantoin in female participants with acute cystitis	Treatment-emergent AEs (TEAEs) and serious AEs (SAEs) and change from baseline results for clinical laboratory tests and vital sign measurements

CCI

Objectives	Endpoints
CCI 	

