8.4. Vital Signs and Electrocardiogram (ECG)

The analyses of non-laboratory safety test results including ECGs and vital signs will be based on GSK Core Data Standards, unless otherwise specified.

Summary Tables will be provided for vital signs change from baseline values, and worst post-baseline vital signs results relative to baseline results. Subjects with missing baseline values are assumed to have within range baseline values. A subject listing will be provided for vital sign values of potential clinical importance defined in [Appendix 6: Values of Potential Clinical Importance](#).

The arithmetic mean of the three recorded ECG measurements will be employed in all data summaries and subject listings. ECG measurements including heart rate, PR interval, QRS duration, QT interval, QRS axis and RR interval will be recorded at Baseline and OT visits (for first approximately 1200 participants enrolled). Corrected QT intervals will be calculated by Bazett's formula:

$$QTcB \text{ (msec)} = \frac{QT}{\sqrt{RR/1000}}$$

and by Fridericia's formula:

$$QTcF \text{ (msec)} = \frac{QT}{\sqrt[3]{RR/1000}}$$

depending on the availability of other measurements.

A summary of the maximum actual and change from baseline value for corrected QT interval will be presented using central reads (BioTel) only. In this shift analysis, the following categories will be used: ≤ 450 , >450 to ≤ 480 , >480 to ≤ 500 , >500 msec. Subject listings will be provided for abnormal baseline and post-baseline ECG findings and ECG values of potential clinical importance as defined in [Appendix 6](#).

The details of data displays are presented in [Appendix 9](#).

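### The SAP drops ECG change from baseline from the secondary safety endpoint without a visible declaration and tabulates only corrected QT, so PR, QRS, uncorrected QT and ECG heart rate get no by-arm summary

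*SAP*

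**What the plan says.** **Protocol.** The secondary safety endpoint in Section 3 covers treatment-emergent and serious adverse events and "change from baseline results for clinical laboratory tests, electrocardiograms (ECGs), and vital sign measurements". The synopsis carries the same endpoint. The safety row of Protocol Table 1 repeats it as "change from baseline results for clinical laboratory tests, ECGs, and vital sign measurements", with summary statistics to be given in each arm separately. Section 9.4.3 states the analysis: "Change from baseline over time in laboratory parameters, ECGs, and vital signs will be summarized with descriptive statistics", and adds that the ECGs will be centrally overread for this purpose.

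**SAP.** Section 2.2 gives the endpoint as adverse events and "change from baseline results for clinical laboratory tests and vital sign measurements". The safety row of Table 1 in Section 2.2.2 has "change from baseline results for clinical laboratory tests, and vital sign measurements". ECGs appear in neither. Section 2.1 opens with "Changes to the planned statistical analysis specified in the protocol (Dated: 03-NOV-2021) are listed below", and no visible item there concerns ECGs. The revision chronology in Section 1 does not mention them either.

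SAP 8.4 names heart rate, PR, QRS, QT, QRS axis and RR as recorded at Baseline and On-therapy, averaged over the triplicate. The summary it specifies is narrower: "A summary of the maximum actual and change from baseline value for corrected QT interval will be presented using central reads (BioTel) only". In the display list (Appendix 9) the only ECG table is Table 3.33, on corrected QT. The remaining ECG output is Listings 41 and 42, which are restricted to participants with an abnormal finding or a value of potential clinical importance.

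**The concern.** A secondary endpoint component defined in the protocol has gone from the SAP's endpoint wording in two places, and the section meant to record such departures is silent in its visible text. Someone programming from the SAP would produce QTc and nothing else by arm from the ECGs.

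What would be missing is a comparison of average shifts. Listings of flagged participants cannot show whether PR, QRS or QT moved by a few milliseconds in one arm relative to the other.

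The protocol gives some reason to want those summaries. Its risk table (2.3.1) describes a reversible QRS increase in monkeys at the highest dose and heart rate and QT effects in the thorough QTc study. It also notes that increased cholinergic effects can potentially be associated with atrioventricular block, while stating that no causal link with gepotidacin has been established. ECG heart rate also bears on reading the QTc table, because RR enters both correction formulas in SAP 8.4.

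**Working it through.** No stated figure is in dispute, so the check is mainly a comparison of texts.

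| Item | Protocol | SAP |
|---|---|---|
| Secondary safety endpoint | ECGs included (Synopsis, Section 3) | ECGs absent (2.2) |
| Estimand table, safety variable | ECGs included (Table 1) | ECGs absent (Table 1) |
| Planned ECG analysis | Descriptive change from baseline for ECGs, no parameter singled out (9.4.3) | Corrected QT only (8.4) |
| Declaration of change | not applicable | No visible item (2.1; revision chronology) |

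Coverage in the SAP's outputs, parameter by parameter:

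| Parameter | By-arm summary in the SAP |
|---|---|
| QTc | Yes: Table 3.33, maximum value and change |
| Pulse rate (vital sign) | Yes: Tables 3.31 (worst case) and 3.32 (change from baseline) |
| ECG heart rate, about 2 hours postdose | None |
| PR, QRS | None; Appendix 6 limits feed Listing 42 |
| Uncorrected QT | None |

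SAP 8.4 says that ECG analyses follow the sponsor's core data standards unless otherwise specified. That does not supply the missing summaries, because the display list contains no further ECG table and no ECG figure.

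Would the data support such a table? Protocol 1.3 and 8.2.3 require On-therapy triplicate ECGs in about the first 1200 participants. At 1:1 allocation that is 1200 / 2 = 600 per arm. The 95% half-width for a difference in mean change is 1.96 × SD × √(2/600). The documents give no SD, so a range is assumed:

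| Assumed SD (bpm or msec) | Half-width |
|---|---|
| 5 | 0.57 |
| 8 | 0.91 |
| 10 | 1.13 |
| 15 | 1.70 |
| 20 | 2.26 |

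For example, 1.96 × 10 × √(2/600) = 1.13. This shows only that the planned data could describe small average shifts. It does not measure a loss, and says nothing about whether a shift exists.

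**The case against.** The strongest reply is that little of importance is lost.

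- **Heart rate.** A reader might infer that heart rate is not compared between arms at all. The documents do not support that. Pulse rate is a vital sign (Protocol 8.2.2), measured at Baseline, On-therapy and Test-of-Cure. SAP Appendix 6 sets heart-rate limits under vital signs, and Tables 3.31 and 3.32 summarise vital signs by arm. Only the ECG reading is untabulated. It differs in being timed near the expected peak concentration; the protocol sets no postdose time for vital signs, although they may often be taken at around the same time as the ECG.
- **Endpoint left unanswered.** A reader might infer that the ECG part of the endpoint goes unanalysed. It does not: QTc change from baseline stays in Table 3.33, from central reads.
- **Known drug effects.** A reader might take the thorough QTc study's rise of about 6 to 10 bpm as a reason to expect a missed signal. That figure comes from 1000 and 1800 mg infusions over 2 hours, not from this oral regimen, and pulse rate is tabulated anyway. For PR and QRS, Protocol 2.3.1 reports no clinically relevant effect in Phase I and II; the QRS finding is nonclinical.
- **Other coverage.** Clinically significant ECG changes are reported as adverse events (Protocol 8.2.3). The cardiovascular terms of special interest include atrioventricular block and bundle branch block, summarised in Table 3.15.
- **Discretion.** Protocol 9.4.3 names no individual ECG parameters, and Sections 9 and 9.4 leave detail to the analysis plan.

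The first four points stand and limit the consequences. The last stands in part. The analysis plan may choose the form of the summaries, but that does not explain removing ECGs from the endpoint and estimand wording. Nor does a QTc-only table naturally answer a commitment made for ECGs alongside laboratory parameters and vital signs. Adverse event counts capture clinically significant changes, not average ones.

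**Conclusion.** The mismatch is real. ECG change from baseline is in the protocol's secondary safety endpoint and estimand table, and is absent from both in the SAP. Following the SAP as written would give no by-arm summary of PR, QRS, uncorrected QT or ECG heart rate.

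Its size is modest. It touches no hypothesis test, error rate or sample size. The human effects the protocol describes, on heart rate and QT, each keep a by-arm table in some form, and nothing in the documents shows that a PR or QRS effect is likely. The case rests on keeping a declared endpoint intact, not on an expected safety signal.

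One qualification concerns disclosure. A reader might conclude that the change was never declared. One item in SAP 2.1, on added exploratory endpoints, is partly blacked out, and the exploratory objectives are redacted. That would be an odd place to record the removal of a secondary safety variable, but the absence of a declaration can be confirmed only for the visible text.

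**What to change.** Restore ECGs to the safety endpoint in SAP 2.2 and to the safety row of SAP Table 1, so that both match the protocol. Add one by-arm descriptive table to SAP 8.4 and the display list, giving Baseline, On-therapy and change from baseline for ECG heart rate, PR, QRS, QT and QTcF, using the triplicate mean and the central read. Finalise this before unblinding.

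If the sponsor prefers to keep the narrower analysis, the minimum is to state and justify it as a departure in SAP 2.1. That would settle the disclosure question but would not restore the summaries.

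The cost is a wording change and one extra table. The recordings and central overread are already planned, so no visit or procedure is added.
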